5.0 Study Procedures

5.1 Study Design

Research Design: A multi-center, repeat-measures randomized controlled mixed-methods trial.

Study Population: The proposed study will focus on Internal Medicine physicians who are part of inpatient care teams and nurses providing care on medical and medical/surgical units at LTC Charles S. Kettles VAMC in Ann Arbor, MI and MEDVAMC in Houston, TX. Medical students, surgical physicians, and physicians on sub-specialty teams will not be included. At both participating facilities the inpatient care teams are predominately composed of 1 attending, 1 senior resident, 2 interns, and up to 3 medical or physician assistant students. Interns and senior residents are usually assigned to a team for 4-week blocks (occasionally 2 weeks), while attendings rotate approximately every 2 weeks. The Ann Arbor VAMC has 3 medical or medical/surgical inpatient units, while MEDVAMC has 5 units. At both facilities each nursing unit employs between 20-30 nurses. We will aim to recruit approximately 30 attendings, 72 residents and 40 nurses at Ann Arbor VAMC. As MEDVAMC is larger, with a greater number of inpatient care teams and nursing units than the Ann Arbor VAMC, we will aim to recruit approximately 40 attendings, 72 residents and 90 nurses. Our target study sample size is a total of 344 physicians and nurses (167 intervention/177 control). For Aim 3, we plan to interview approximately 8 physician team members and 4-6 nurses from the intervention arm at each site.

General Study Overview and Outcome Measures:

A summary of the proposed study activities at each participating site is presented in **Table 2** below.

Table 2: Overview of Study Activities at Each Study Site

| Study Detail | Physicians | Nurses |
|----------------------------------|--|--|
| Target | Attendings, senior residents and interns on inpatient medicine teams | Nurses on medical or medical/surgical units |
| Teams/Units Participating | 2 teams each month for 12 months randomized to intervention or control arm at each site | 2 units (1 intervention; 1 control) at Ann Arbor VAMC & 4 units (2 intervention; 2 control) at MEDVAMC randomized once & followed for 12-months |
| Estimated number of participants | 107 intervention and 107 control | 20 intervention and 20 control at Ann Arbor VAMC; 40 intervention and 50 control at MEDVAMC |
| Habituation Period | 1 month | 1 month |

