5.6 Data Analysis

Quantitative Statistical Analysis (Aims 1 and 2): Differences in hand hygiene adherence and duration between intervention and control groups will be assessed using Fisher's exact test and t-test, as appropriate. Risk differences in adherence to duration of hand hygiene will be calculated for both intervention and control groups. Because the primary outcomes for Aim 1 (i.e., hand hygiene adherence and duration) are expected to occur frequently, we will use generalized linear models to evaluate differences in hand hygiene adherence and duration for the intervention versus control group, with the Poisson distribution (log link) and robust error variance. Models will account for provider type and level, and will incorporate clustering by physician team (and separately for nursing unit). Statistical significance will be calculated for the intervention (intervention vs. control) coefficient.

As a secondary outcome for Aim 1, we will assess changes and differences in hand hygiene perception based on response to select questions from PSHW. For Aim 2, mindfulness will be based on responses to FFMQ and well-being will be based on responses to WBI. FFMQ and WBI scales will be scored according to the published algorithms. Descriptive statistics will be used to summarize participant scores from pre- and post-intervention, as well as 6-month post-intervention follow-up assessments. Within-group paired-samples t-tests will be used to test for improvement in participant scores across the baseline, post-intervention (~14 days for physicians and 1-month for nurses), and 6-month post-intervention follow-up periods, for the intervention and control groups separately. Analyses will use list-wise deletion for missing data. Participants not completing all surveys will still be included in any analysis for which they provide data. For all analyses, p values less than 0.05 will be considered significant and all tests will be two-tailed. Analysis of covariance (ANCOVA) models will then be used to assess relative changes in mindfulness, well-being, and hand hygiene perceptions across groups, the most direct test of discriminant validity. In these models, post-test scores will be predicted by group status controlling for pre-test scores.

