Power - Based on a range of 10%-15% significant percent change in hand hygiene adherence from our pilot data,⁷² we are anticipating an expected increase in hand hygiene adherence due to the intervention from approximately 80% at baseline to 88%-92% at follow-up. We will have 79.8% power to detect this 10% increase based on a fixed total sample size of 334 with a two-sided alpha of 0.05, assuming an average of 60 observed hand hygiene opportunities per provider per measurement time point (i.e., intervention and follow-up), and taking into account clustering of data within site/team/unit (assumed Intraclass Correlation Coefficient=0.4).⁸² For assessing differences in the select PSHW questions we will have 70.1% power to detect an effect size of 0.15.⁸³ For assessing differences in FFMQ and WBI scores, we will have >95% power to detect effect sizes ranging from 0.3 to 0.75 as found in prior studies.^{65,84,85}

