Mindful Hand Hygiene to
Reduce Infections Among
Veterans While Enhancing
Provider Well-Being

NCT05261282

December 5, 2025

Data Analysis Plan

Differences in hand hygiene adherence and duration between intervention and control groups will be assessed using Fisher's exact test and t-test, as appropriate. Differences in adherence to duration of hand hygiene will be calculated for both intervention and control groups. As a secondary outcome for Aim 1, the investigators will assess changes and differences in hand hygiene perception based on responses to select questions from the PSHW. For Aim 2, mindfulness will be based on responses to the FFMQ and well-being will be based on responses to the WBI. Survey scales will be scored according to the published algorithms. Descriptive statistics will be used to summarize participant scores from baseline and post-intervention, as well as 6-month post-intervention (sustainability) follow-up assessments. Within-group paired-samples t-tests will be used to test for improvement in participant scores across the baseline, post-intervention (~14 days for physicians and 1-month for nurses), and 6-month post-intervention (sustainability) follow-up periods, for the intervention and control groups separately. Participants not completing all surveys will still be included in any analysis for which they provide data. Listwise deletion for observations containing less than 85% complete responses for the FFMQ or WBI items will be used. Missing values for observations with at least 85% responses for the FFMQ or WBI items will be imputed using the average value obtained from non-missing values within each respective subscale. Multilevel linear mixed regression models will be used to assess changes in mindfulness and well-being across groups and the effectiveness of the intervention. Mixed models account for correlation between repeat measurements on the same participant and accommodate missing data across time points. Random effects will be modeled to account for clustering of survey responses at the clinician level. All models will be adjusted for fixed effects for clinician role (physician/nurse) and intervention fidelity. For all analyses, p-values less than 0.05 will be considered significant and all tests will be two-tailed.

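### The survey power figures (70.1% at 0.15 for PSHW, above 95% from 0.3 for FFMQ and WBI) cannot be reproduced from the documented inputs for the between-arm comparison

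*Protocol*

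**What the plan says.** The Power paragraph of Protocol section 5.6 makes two survey claims. For PSHW: "For assessing differences in the select PSHW questions we will have 70.1% power to detect an effect size of 0.15". For FFMQ and WBI: "we will have >95% power to detect effect sizes ranging from 0.3 to 0.75". Neither sentence names a test or an effect-size metric.

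The numerical inputs in that paragraph belong to the hand hygiene adherence calculation. It uses a "fixed total sample size of 334 with a two-sided alpha of 0.05" and an ICC of 0.4 for site, team and unit. Section 5.1 gives a slightly different total: "Our target study sample size is a total of 344 physicians and nurses (167 intervention/177 control").

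Two kinds of survey test are planned. Both documents plan paired t-tests within each arm. For the comparison between arms the protocol plans ANCOVA for all three instruments: "In these models, post-test scores will be predicted by group status controlling for pre-test scores". The SAP plans mixed models for FFMQ and WBI: "Multilevel linear mixed regression models will be used to assess changes in mindfulness and well-being across groups and the effectiveness of the intervention". Section 5.6 makes PSHW a secondary outcome of Aim 1; FFMQ and WBI belong to Aim 2.

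**The concern.** Aims 1 and 2 ask whether the intervention works, so the relevant power is that of the randomised comparison. With about 167 people per arm, a standardised difference of 0.15 is small, and 70% power for it looks high. More than 95% at 0.3 also looks high unless baseline adjustment removes much of the variance.

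The survey sentences are also silent on two things that lower power. Randomisation is by physician team and nursing unit, with only six units, and the guided discussions are held in groups. Follow-up surveys go by email to physicians who may have rotated elsewhere, and the protocol's analysis uses list-wise deletion.

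At stake is how a null result is read. If power at 0.3 is believed to exceed 95%, a non-significant FFMQ or WBI result looks close to conclusive at the bottom of the protocol's own effect range. For PSHW, a true effect of 0.15 could be missed far more often than the stated 30%.

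**Working it through.** **Inputs from the documents.** Two-sided alpha 0.05; N = 334 (taken as 167 per arm) or 344 (167 and 177). Nurses: 130 in 6 units. Physicians: 214, in 48 teams by Table 2 (2 teams x 12 months x 2 sites).

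**Assumptions, because the documents give no value.** Pre-post correlation r, response rate and survey ICC. The effect size is first read as a standardised mean difference d.

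**Formula.** Noncentrality L = d / sqrt[(1 - r^2) x D x (1/n1 + 1/n2)], with power from the noncentral t on n1 + n2 - 2 degrees of freedom (critical value 1.967). The clustering factor is D = 1 + (m - 1) x ICC, and D = 1 without clustering.

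**1. Unadjusted two-arm comparison (r = 0, D = 1).**
- 167 v 167: sqrt(1/167 + 1/167) = 0.1094. At 0.3, L = 2.74 and power is 78.0%. At 0.15, L = 1.37 and power is 27.7%.
- 167 v 177: sqrt(1/167 + 1/177) = 0.1079. At 0.3, L = 2.78 and power is 79.2%. At 0.15, L = 1.39 and power is 28.4%.

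Neither stated figure is reproduced.

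**2. Within-arm paired t-test, n = 167, L = d x sqrt(167), with d now the standardised mean change.** At 0.3, L = 3.88 and power is 97.1%, which meets the FFMQ/WBI claim. At 0.15, L = 1.94 and power is 48.7%, which does not give 70.1%. This test does not compare the arms.

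**3. ANCOVA on one post-baseline score, no loss, no clustering.**

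| r | 0.15 (N 334 / 344) | 0.3 (N 334 / 344) |
|---|---|---|
| 0.5 | 35.2% / 36.0% | 88.4% / 89.3% |
| 0.7 | 48.2% / 49.3% | 96.9% / 97.3% |

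Solving for r: 95% power needs L of about 1.967 + 1.645 = 3.61. At 0.3 with N = 334, sqrt(1 - r^2) = 2.741/3.61 = 0.759, so r = 0.65 (0.64 with N = 344). For 70.1% power, L is about 1.967 + 0.527 = 2.494. At 0.15, sqrt(1 - r^2) = 1.371/2.494 = 0.550, so r = 0.84 (0.83 with N = 344).

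**4. Unadjusted d detectable with 95% power.** 3.61 x 0.1094 = 0.395 (N = 334), or 3.61 x 0.1079 = 0.390 (N = 344). At d = 0.4 with N = 334, power is 95.4%.

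**5. Loss and clustering, ANCOVA, N = 344, assumed 80% response.** The size-weighted mean cluster is m = (214^2/48 + 130^2/6)/344 = (954.1 + 2816.7)/344 = 10.96. For example, with ICC 0.02, D = 1 + 9.96 x 0.02 = 1.199.

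| Survey ICC (assumed) | 0.15, r = 0.5 / 0.7 | 0.3, r = 0.5 / 0.7 |
|---|---|---|
| 0 | 30% / 41% | 82% / 93% |
| 0.02 | 26% / 35% | 74% / 89% |
| 0.05 | 22% / 29% | 65% / 81% |

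**6. Cohen's f.** For two equal groups f = d/2, so f = 0.15 is d = 0.3 and f = 0.3 is d = 0.6. With N = 334, power is 78.0% at f = 0.15 and above 99.9% at f = 0.3. Power of 70.1% at f = 0.15 corresponds to about 277 analysed participants.

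**The case against.** The strongest reply is that the planned comparison is baseline-adjusted, so the unadjusted 78-79% is not its power. This stands for FFMQ and WBI. With r of about 0.65 or more, complete response and no clustering, ANCOVA exceeds 95% at 0.3. The SAP's mixed model also uses both post-baseline scores. If its contrast were their baseline-adjusted mean, with equal correlations r across the three time points, the variance factor is (1 + r)/2 - r^2. This is largest at r = 0.25, where it equals 0.5625; power at 0.3 is then 95.4% (N = 334) with no loss or clustering. The SAP does not say that this average is its contrast, and an assumed 80% response lowers the figure to about 90-91%. The same contrast at 0.15 gives 49% (r = 0.5) to 62% (r = 0.7), so it does not rescue the PSHW figure.

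The protocol also never says that its effect sizes are d. On a Cohen's f scale both figures may be attainable. That is a reason to name the metric, not evidence that f was used.

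A reader might infer that the figures came from a pooled pre-post test on 275 people, since 275 is 80% of 344 and such a test gives 70.1% at 0.15 by the normal approximation. The documents do not support this. They state no 80% rate, the power paragraph uses 334, and a two-group ANCOVA on Cohen's f with about 277 people fits equally well.

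**Conclusion.** With the documented sample size and alpha, and effects read as d, none of the tests checked gives both figures without assumptions that the protocol does not state. With no loss and no clustering, between-arm power at 0.15 is 28% unadjusted and 35-36% at an assumed r of 0.5, against a stated 70.1%. At 0.3 it is 78-79% and 88-89%, against a stated value above 95%. With an assumed 80% response and survey ICC of 0.02, it is about 26-35% at 0.15 and 74-89% at 0.3, for r from 0.5 to 0.7.

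A reader might go further and infer that Aim 2 as a whole is much less well powered than claimed. The documents do not support that. The FFMQ/WBI shortfall lies only below about d = 0.4 (unadjusted, no loss, no clustering) in a stated range that runs to 0.75, and a high enough r removes it. The large gap belongs to PSHW, an Aim 1 secondary outcome. Nor is the claim shown to be impossible: it depends on a metric, correlation, response rate and ICC that are not given. The difference between 334 and 344 moves these figures by only about one percentage point.

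**What to change.** Recompute both survey figures for the between-arm contrast that will be tested: ANCOVA for PSHW, and the SAP mixed model for FFMQ and WBI, with its time-point contrast named. State the effect-size metric, the assumed pre-post correlation, the expected response at each survey and the ICC for team and unit. Give power as a range over those assumptions. Keep the above-95% statement only for effect sizes where it holds under them; unadjusted, with no loss or clustering, that is from about d = 0.4. If the figures are on a Cohen's f scale, or refer to the within-arm paired tests, say so.

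The cost is protocol and SAP wording, with no added participants. The downside is a stated power that will probably be less favourable, most visibly for PSHW.

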5.7 Withdrawal of Subjects

Subjects may choose to withdraw at any time without any penalty. We will use the data collected up until the point of withdrawal. There are no anticipated circumstances for subject withdrawal without subject consent.

6.0 Reporting

Because this is a minimal risk study with no patient involvement, we do not anticipate any serious adverse events. Study subjects will be physicians and nurses who will be asked to complete either paper or electronic surveys, participate in group led discussions, complete online training modules, and use an optional mobile application on mindfulness. Hand hygiene compliance will be monitored covertly. Intervention participants will be encouraged to practice mindfulness and use hand hygiene as a moment of mindfulness. Serious adverse events (SAEs) to be monitored include the following: 1) a breach of a participant's confidentiality or privacy that involves potential risk to that participant or others, 2) deviations from VA IRB regulations and policies, and 3) unanticipated problems that involve social or economic harm instead of the physical or psychological harm associated with (UAPs) adverse events. SAEs will be prospectively tracked according to the following plan: reports of SAEs and protocol deviations will be made by the study team member who discovers the event, the site PI, or site project manager (if applicable) to the primary site (Ann Arbor) project manager. The primary site project manager and PI will report the event to the Central IRB (Primary Site IRB). Any SAEs and UAPs meeting the definition of serious will be reported within 5 business days of discovery to the Central IRB. AEs and UAPs that do not meet the definition of serious are to be reported to Ann Arbor project manager as they are discovered, and will be reported to the Central IRB in summary at the time of continuing review/project closure. Protocol deviations/violations that are likely to substantially adversely affect 1) the rights, safety, or welfare of a participant; 2) a participant's willingness to continue participation; or 3) the integrity of the research data, including VA information security requirements will all be reported within 5 working days of being made aware of the occurrence. [name] will be involved with all decisions related to the health and safety of subjects for this project. We will also submit annual progress reports to the HSR&D Data Safety and Monitoring Board.

7.0 Privacy and Confidentiality

- Will you be accessing REAL SSNs? **NO**

The study will not use or disclose any protected health information (PHI). To protect subjects' confidentiality, all study materials will be labeled using unique study ID codes only. For example, participant names or other individual names will not appear in any of the surveys or interview transcripts. If such information is volunteered (despite instructions) in a taped session or in a survey, it will be removed by the transcriptionist and/or other research staff. Files that link the interviewee with a study ID will be securely stored in a restricted access folder on a secure VA CCMR server. The original audio recordings and study transcripts will also be electronically stored in restricted access folders on secure servers that can only be accessed by specified study personnel. At the end of the study, the linking information will be removed from the transcripts to protect confidentiality. Any notes taken during the interviews and/or guided sessions will be typed up and stored on the secure CCMR Server in the study folder. Hard copies of the notes will be stored in locked filing cabinets in the CCMR Suite on the [name]. Once the handwritten notes are typed up and checked for accuracy, the hard copies will be destroyed using the VA shredding service. For all study data, we will follow approved VA guidelines, Records Control Schedule RCS 10-1, for the disposition of records following closure of the study.

8.0 Communication Plan

Communication will occur through regular study team meetings. These monthly meetings will include discussion of the events since the prior meeting, and specifically if any problems/events have occurred. The PIs and the study team will work to address any problems/events to reduce the likelihood of occurrence in the future, to keep the risk to subjects as low as possible, and to maximize the potential study benefits. These team meetings will also be utilized to ensure that all relevant IRB policies and study procedures are being followed. These include: (1) all participants understand, agree to and provide informed consent (written or verbal as approved by the IRB) before participating; (2) strict adherence to a participant's right to withdraw or refuse to answer questions will be maintained; (3) all data collection is completely confidential; (4) consent forms and identifying information are kept separate from the actual participant data; (6) all identifying information is kept locked at all times and sensitive computer files are maintained on a secured VA server; and (7) participants are informed in writing how to contact the site PD/PI, the study coordinator, and IRB office with any questions and/or concerns. Additional communication about the project will be conducted over email. [name], [name], and the project manager will remain in close contact regarding all multi-site study activities including recruitment procedures, recruitment status, intervention implementation, data collection and subject follow-up.

Mindful Hand Hygiene to
Reduce Infections Among
Veterans While Enhancing
Provider Well-Being

NCT05261282

December 5, 2025

Data Analysis Plan

Differences in hand hygiene adherence and duration between intervention and control groups will be assessed using Fisher's exact test and t-test, as appropriate. Differences in adherence to duration of hand hygiene will be calculated for both intervention and control groups. As a secondary outcome for Aim 1, the investigators will assess changes and differences in hand hygiene perception based on responses to select questions from the PSHW. For Aim 2, mindfulness will be based on responses to the FFMQ and well-being will be based on responses to the WBI. Survey scales will be scored according to the published algorithms. Descriptive statistics will be used to summarize participant scores from baseline and post-intervention, as well as 6-month post-intervention (sustainability) follow-up assessments. Within-group paired-samples t-tests will be used to test for improvement in participant scores across the baseline, post-intervention (~14 days for physicians and 1-month for nurses), and 6-month post-intervention (sustainability) follow-up periods, for the intervention and control groups separately. Participants not completing all surveys will still be included in any analysis for which they provide data. Listwise deletion for observations containing less than 85% complete responses for the FFMQ or WBI items will be used. Missing values for observations with at least 85% responses for the FFMQ or WBI items will be imputed using the average value obtained from non-missing values within each respective subscale. Multilevel linear mixed regression models will be used to assess changes in mindfulness and well-being across groups and the effectiveness of the intervention. Mixed models account for correlation between repeat measurements on the same participant and accommodate missing data across time points. Random effects will be modeled to account for clustering of survey responses at the clinician level. All models will be adjusted for fixed effects for clinician role (physician/nurse) and intervention fidelity. For all analyses, p-values less than 0.05 will be considered significant and all tests will be two-tailed.

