Randomization – At each study site the participating physician teams and nursing units will be randomly assigned into one of two study arms (intervention/control). For physician teams, this will occur on a rolling basis for 12 months with 2 physician teams randomly selected at each site each month for participation (1 intervention, 1 control). Once randomized, an email will be sent to the initial attending of the team introducing the study and asking them to reply to the email if they would prefer to opt out and not have their team participate in the randomized controlled trial. If the attending physician from a team refuses to allow their team to participate, the next team identified from the randomized list will be approached to participate. If a new attending joins the team mid-month, they will be approached to participate in the study, but will be automatically assigned to the same randomization group as the rest of their team.

Similarly, a total of 2 medical/surgical units from VAAHS (1 intervention, 1 control) and 4 medical/surgical units from MEDVAMC (2 intervention, 2 control) will be randomly selected to participate in the nurse portion of the project. The nurse manager for each

selected unit will then be approached to obtain approval for the unit to participate. If a nurse manager declines, the next unit on the list will be selected.

For both physicians and nurses, an independent statistician will allocate the teams and units in a concealed fashion, using a computer-generated randomization schema. The physicians and nurses from the intervention groups will receive both independent and group-facilitated mindfulness education, will be encouraged to use a mindfulness mobile app as a practice reminder and additional resource, and instructed to integrate moments of mindfulness with repeated episodes of hand hygiene during the course of caring for patients. The control groups will receive no such education or intervention and will continue as usual.

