There could be a risk of a Hawthorne effect with conducting hand hygiene observations. Three basic, non-technological methods to help avoid or decrease the Hawthorne effect include: 1) letting healthcare workers habituate to unobtrusive and/or frequent observation; 2) using indirect methods to monitor hand hygiene adherence, such as monitoring consumption of hand sanitizer products; and 3) covertly observing hand hygiene adherence.⁸¹ To minimize the risk of Hawthorne effects for this project, research assistants will conduct wash-in period observations within units as a means of habituating physicians and nurses to being observed. Additionally, research assistants will not follow the inpatient teams. Instead, all observations will be done covertly from a randomly chosen location on one of the hospital units each day. As such, we anticipate that research assistants will be able to capture hand hygiene moments for 4-6 patient encounters per observation day. Due to the variable number of patients, team attendance and daily rounding structure, each day we expect to observe approximately 8-24 before room entry and 4-12 after room exit hand hygiene moments, with an additional 2-3 measures of attending hand hygiene duration upon leaving the room. With roughly 10 observational days per attending team (M-F, no weekend or holiday observations) during the intervention period and up to 24 attending teams, we estimate we will collect the following physician data per arm at each site: 1,920-5,670 room entry hand hygiene moments, 960-2,880 room exit hand hygiene moments, and 480-720 measurements of hand hygiene duration.

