Covert observations within randomly selected areas within units will also be conducted for observing hand hygiene among nurse participants. Observations will be conducted for 1 month before the intervention and 1-month after the intervention. On all participating units, observations of nurse hand hygiene while entering and exiting patient rooms will be conducted. Hand hygiene duration among all nurses will also be captured upon room exit. Nurses will be observed for approximately 4 hours per day during the first part of their shift, as all nurses typically check in with each patient at the start of their shift. From covert locations within the unit, the observers will only be able to observe approximately 10 rooms at a time. They will move their location in the unit each day to ensure representation from different nurses. The number of times a nurse enters each patient room will vary, but we estimate at minimum each nurse will enter each room once per hour. Therefore, observing 10 patient rooms for 4 hours per day, with 2 observation points per entry would lead to approximately 80 hand hygiene moments observed per day per unit. Observing 3 units per arm for approximately 44 days total would lead to an estimated 7,040 nurse hand hygiene observations per study arm in total. As hand hygiene duration will also be recorded upon room exit, and estimated total of 3520 hand hygiene duration observations per study arm will be observed. In addition to the 1-month post-intervention observation period, we will also observe and collect 1 month of data on hand hygiene moments at 1-year post-intervention in the intervention and control units at both sites.

Collected data will be transferred from the paper observation data tool into a study database. The data analyst and project manager will be able to link these covert observations accordingly to intervention or control groups based on team and unit name.

Study surveys will be distributed in person using a paper survey and a postage-paid business reply envelope where feasible. Electronic surveys containing questions from FFMQ, WBI, and PSHW surveys will be generated. Study participants will be directed to a link to the survey tool (for the pre- and post-intervention, as well as 6-month post-intervention follow-up periods) and responses will be saved to a database managed by the study team.

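### The SAP tests the two primary hand hygiene outcomes with Fisher's exact test and a t-test, and omits the protocol's model clustered on the randomised team or unit

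*SAP*

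**What the plan says.** Randomisation is by cluster. Protocol section 5.1 (Randomization) states: "At each study site the participating physician teams and nursing units will be randomly assigned into one of two study arms (intervention/control".

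Protocol section 5.6 names adherence and duration as the Aim 1 primary outcomes. It opens with Fisher's exact test and the t-test, then specifies generalized linear models (Poisson, log link, robust error variance) for both. On clustering it says: "Models will account for provider type and level, and will incorporate clustering by physician team (and separately for nursing unit"). On inference it says: "Statistical significance will be calculated for the intervention (intervention vs. control) coefficient". The power paragraph of the same section also allows for clustering, "taking into account clustering of data within site/team/unit (assumed Intraclass Correlation Coefficient=0.4").

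The SAP, dated December 2025, repeats the opening sentence: "Differences in hand hygiene adherence and duration between intervention and control groups will be assessed using Fisher's exact test and t-test, as appropriate". It contains no Poisson or other model for hand hygiene and no clustering by team or unit. Its only regression models are linear mixed models for mindfulness and well-being, of which it says: "Random effects will be modeled to account for clustering of survey responses at the clinician level". It applies the two-sided 0.05 threshold to every analysis. It does not say that it replaces section 5.6, or that the section 5.6 model still applies.

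**The concern.** Hand hygiene moments from one team or one unit share people, leadership, ward layout and the allocated arm, so they are not independent. Fisher's exact test on pooled moments treats each as a separately randomised subject, and so does a t-test on single duration measurements. The standard error is then too small, and an intervention with no effect can readily be declared effective.

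The SAP's clinician-level random effects do not help. They concern survey scores, not hand hygiene, and the clinician is not the randomised unit. For duration, the SAP also does not say whether the t-test is on single measurements or on team or unit means.

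With two analyses on paper and no order of precedence, the choice could be made after the results are seen.

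**Working it through.** **Plan's own figure.** The power paragraph gives 79.8% for 80% v 88%, N = 334, 60 moments per provider and ICC 0.4. With a design effect DE = 1 + (m − 1) × ICC = 1 + 59 × 0.4 = 24.6, the effective n per arm is 167 × 60 / 24.6 = 407 and power is 87.7%. The 79.8% is not reproduced. That is a separate matter; only the ICC is used below.

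**Inputs (protocol section 5.1 unless stated).** The counts are not consistent within the protocol, so alternatives are carried through.
- Teams: one intervention and one control team per site per month, 12 months, 2 sites = 24 per arm. Section 5.2 implies 36 per arm (one team at Ann Arbor and two at Houston per month per arm).
- Moments per team: lower bounds per arm per site, (1,920 + 960) / 12 randomised teams = 240.
- Nurse moments: "Observing 3 units per arm for approximately 44 days total would lead to an estimated 7,040 nurse hand hygiene observations per study arm". 7,040 / (3 units × 2 months) = 1,173 per unit-month. The stated components give 80 × 44 × 3 = 10,560, or 1,760 per unit-month.
- Attending duration: "480-720 measurements of hand hygiene duration" per arm per site. 480/12 = 40 to 720/12 = 60 per team.
- Nurse duration: 3,520 / 6 = 587 per unit-month.
- ICC: 0.4 is the only documented value; 0.05 and 0.01 are assumptions.

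**Adherence, no true effect (80% in both arms).** Cluster rates were drawn from a beta distribution and moments from a binomial, with 20,000 runs and an observation-level 2×2 z-test at two-sided 5%. At these sample sizes the z-test stands in closely for Fisher's test. Rejection rates:

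| Clusters × moments per arm | ICC 0.4 | 0.05 | 0.01 |
|---|---|---|---|
| 24 × 240 + 3 × 1,173 | 0.90 | 0.72 | 0.45 |
| 24 × 240 + 3 × 1,760 | 0.92 | 0.78 | 0.55 |
| 36 × 240 + 3 × 1,173 | 0.89 | 0.71 | 0.42 |
| 48 × 120 + 3 × 1,173 | 0.89 | 0.71 | 0.44 |
| Physicians only, 24 × 240 | 0.84 | 0.59 | 0.28 |
| Physicians only, 48 × 120 | 0.78 | 0.46 | 0.19 |

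The 48 × 120 rows count each two-week attending period as its own cluster.

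Analytic check for physicians, 24 × 240: DE = 1 + 239 × 0.4 = 96.6, and type I error = 2[1 − Φ(1.96/√96.6)] = 0.84, in agreement.

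**Duration, if the t-test uses single measurements.** Type I error = 2[1 − Φ(1.96/√DE)]:

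| m per cluster | ICC 0.4 | 0.05 | 0.01 |
|---|---|---|---|
| Attendings, 40 | 0.63 | 0.25 | 0.10 |
| Attendings, 60 | 0.69 | 0.32 | 0.12 |
| Nursing unit-month, 587 | 0.90 | 0.72 | 0.45 |

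**Restoring the protocol model is not enough for nurses.** If nurses are modelled separately there are 3 v 3 units. An uncorrected robust variance divides by 3 rather than 2 in each arm, so it is too small by a factor of 2/3. The z-test then rejects with probability P(|t₄| > 1.96 × √(2/3)) = P(|t₄| > 1.60) = 0.185 under the null.

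**The case against.** The best reply is that the clustered analysis is already pre-specified. The Fisher and t-test sentence stands in the protocol beside the model, the one-paragraph SAP nowhere withdraws section 5.6, and the two documents read together contain a valid test. This is right in one respect: the defect is an omission left unreconciled, not a new test introduced by the SAP, and the error rates apply only if the SAP's tests become the inference. It does not remove the problem. The SAP is more than an abridgement: it replaces the protocol's ANCOVA with mixed models, and its list-wise deletion with an 85% completeness rule plus subscale-mean imputation. A reader cannot tell whether dropping the hand hygiene model was equally deliberate.

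Second, an ICC of 0.4 at team or unit level is extreme. At 80% adherence it implies a between-cluster SD of √(0.8 × 0.2 × 0.4) = 0.25, and the protocol pairs the ICC with moments per provider, so its level is unclear. That is fair, and the 90% is best read as the upper end. The conclusion survives at ICC 0.01.

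Third, neither document says that physicians and nurses would be pooled, and counting two-week attending teams gives smaller clusters. Physician adherence error is then 78%, 46% and 19% at the three ICCs. Attending duration with 20–30 measurements gives 50–58%, 16–21% and 7–8%. But the randomised unit is the monthly team, and a second attending joins the arm already allocated. Even on this reading adherence error stays at 19% or more. For attending duration at a small ICC, the error would be modest.

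**Conclusion.** The concern holds and must be fixed before analysis. The textual finding needs no assumption: the SAP drops the only stated between-arm analysis of the two Aim 1 primary outcomes that is tied to the unit of randomisation, and gives no precedence rule.

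The size is conditional on observation-level tests. For adherence, the nominal 5% test would reject a true null about 90% of the time at the protocol's ICC (89–92% across pooled readings of the counts). It would do so 42–55% of the time at an assumed ICC of 0.01, or 19–28% for physicians alone. For duration the size depends on an analysis unit the SAP does not state and an ICC neither document gives. It ranges from slight (attendings, low ICC, small clusters) to about 90% (nursing units at ICC 0.4).

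**What to change.** Revise the SAP so that it agrees with protocol section 5.6:
- Name the analysis clustered on randomised team or unit as the primary inference for both adherence and duration, and say that it governs.
- Label the Fisher and t-tests descriptive, or delete them.
- Keep the protocol's Poisson log-link risk ratio for adherence. The protocol's duration model is also a log-link ratio, so a switch to a mean difference should be declared as a change.
- State the analysis unit for duration.
- For nursing units, use a small-sample correction, or a unit-level analysis with degrees of freedom based on units: 6 − 2 = 4, or 3 if adjusted for site, since units are allocated 1 v 1 and 2 v 2 within site.

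No new data are needed, because section 5.1 already has team or unit name on the observation form. The cost is wider intervals and less power. With 24 teams per arm × 240 moments and ICC 0.4 at team level, the effective n is 5,760 / 96.6 = 60 per arm. Power is then about 22% for 80% v 88% and 48% for 80% v 92%. At an assumed ICC of 0.05 (DE 12.95) it is about 91% for 80% v 88%. These are physician-only figures, so they do not compare directly with the stated 79.8% for the whole sample. A nurse-only 3 v 3 analysis at ICC 0.05, with 1,173 moments per unit and 4 degrees of freedom, has about 15% power for 80% v 88%. The low power comes from the design; the unclustered tests only hide it.
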